7.3.3.2. Missing Baseline Data

Every effort will be made to ensure that accurate baseline information on the patients is collected. In the event that a patient is missing baseline data, the patient will be included in appropriate analysis sets per definition in Section 7.1 but excluded from change from baseline analyses.

7.3.3.3. Missing Relationship and Severity in Adverse Events

During final analysis, adverse event relationships and severity grades will not be imputed. At the end of the study, all missing relationships and severity grades will be queried and completed.

7.3.3.4. Imputation Methods for Missing OCS Dose Data

OCS dosage levels will not be imputed, and those that are recorded as "ongoing" or are missing an end date in the collected OCS information will be assumed to have been taken up to the date of last visit. The data listings will not show an end date.

aTyr Pharma, Inc.
 Study ATYR1923-C-002 Statistical Analysis Plan
 IND#: 133692

FINAL Version 1.0
 2021-08-02

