7.1.6.2. Oral Corticosteroid Taper

Starting on Day 15, patients will begin a taper (reduction) in OCS (per the ATYR1923-C-002 Oral Corticosteroid Taper Guidelines) from their starting dose of 10-25 mg/day of prednisone (or equivalent) to a target dose of 5 mg/day, to be completed on or before Day 50. The OCS dose will be tapered by 5.0 mg/day every 1 to 2 weeks, depending on the starting dose. Smaller incremental titrations to the target dose of 5 mg/day by Day 50 may be implemented per Investigator judgement. Patients will be maintained at the target dose of 5.0 mg/day (or equivalent) through Week 24/EOS. Optionally, further titrations in the OCS dose to below 5 mg/day may be attempted after the Week 16 visit, if determined by the Investigator to be feasible.

Patient will document OCS doses in a diary, which will be reviewed at relevant scheduled telephone contacts and study visits.

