10.1.1. OCS Data Sources

The sources of OCS use are summarized in the table below.

Time of Use	Data Source	CRF Name	Comments
Historical and current use at Screening	OCS LOG	OCS Log - Prior and Current Use table	Historical use will be added here. An additional row for every change in steroid or dose
Steroid use beginning on Day 1	eDiary	Patient Diary	Patients will be entering a form every day and from that data we can pull out any dosing changes or changes in use
	OCS LOG (for subjects who do not have eDiary)	OCS Log - Prior and Current Use table	Study Coordinators will be responsible for recording any dosing changes or changes in steroid use in this table based on the paper diaries completed by the subject

aTyr Pharma, Inc.
 Study ATYR1923-C-002 Statistical Analysis Plan
 IND#: 133692

FINAL Version 1.0
 2021-08-02

Changes in Dose	eDiary and OCS LOG for subjects without eDiary	Patient Diary and OCS Log - Prior and Current Use table	
-----------------	--	---	--

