10.1.3. Time adjusted OCS Burden

Time adjusted AUC is a measure of steroid burden and approximates the mean steroid usage post-baseline for each patient. For each patient, it is calculated and summarized as follows,

$$Time\ Adjusted\ AUC = \sum_{t=M}^{N-1} \frac{AUC}{N-M} = \sum_{t=M}^{N-1} \frac{(C_t + C_{t'}) (t' - t)}{2(N-M)},$$

where

C_x is the OCS dose in mg on day x ,

t' is the study day of the next known OCS daily dose after day t ,

M and N are start and end study days of the analysis periods of interest. In this study, we are interested in the time periods a) Day 1 through end of dosing period (30 days after last dose) or day of last known OCS dose (if earlier than end of dosing period) and b) Day 51 through end of dosing period (30 days after last dose) or day of last known OCS dose (if earlier than end of dosing period).

Similarly, change from baseline and percent change from baseline at each diary entry will be used as C_x in the formula above, and analyses will be repeated.

aTyr Pharma, Inc.
Study ATYR1923-C-002 Statistical Analysis Plan
IND#: 133692

FINAL Version 1.0
2021-08-02

In addition, active treatment arm for each cohort and combined active arm are compared to combined placebo using the following pseudo code.

```
proc glm data = auc;  
  class treatment(ref=Placebo);  
  model auc = treatment baselineOCS / solution;  
  lsmeans treatment / pdiff=control("Placebo") adjust=T cl;  
run;
```

The difference between LS means, 95% Confidence Intervals and p-values will be presented.

Time adjusted AUC for Day 1/51 through end of treatment periods will be summarized using density and box plots by treatment.

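### The SAP carries any OCS record without an end date to the last visit, with no exception for a later dose row, so an open non-final row in the OCS log overlaps its successors

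*SAP*

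**What the plan says.** SAP 7.3.3.4 states that "OCS dosage levels will not be imputed", and then fills in duration: a record marked as ongoing, or "missing an end date in the collected OCS information will be assumed to have been taken up to the date of last visit". Section 10.1 sends the OCS analyses back to that section for missing values.

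The source table in SAP 10.1.1 separates two kinds of patient from Day 1. eDiary patients are described this way: "Patients will be entering a form every day and from that data we can pull out any dosing changes or changes in use". For the rest the source is "OCS LOG (for subjects who do not have eDiary"), where coordinators enter dose changes from paper diaries. The comment "An additional row for every change in steroid or dose" stands in the screening row of that table. The on-study log entries go into the same CRF table and also record changes.

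SAP 10.1.3 computes a time-adjusted AUC from one OCS dose per study day, where the next time point "is the study day of the next known OCS daily dose after day" t. The window closes at the "end of dosing period (30 days after last dose) or day of last known OCS dose (if earlier than end of dosing period"). SAP 10.1.5 uses OCS dose over time for runs of at least 5, 30, 60, 90 and 115 consecutive days at 5 mg or less, for time to first relapse, and for the proportion of days at 5 mg or less.

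**The concern.** Protocol 7.1.6.2 has patients taper from a "starting dose of 10-25 mg/day of prednisone (or equivalent) to a target dose of 5 mg/day" in steps, and Protocol 7.1.6.3 allows a return to 5 mg after rescue. A log patient will therefore usually have several consecutive rows. For any row but the last, the start of the next row is recorded evidence of when the earlier dose stopped. The rule in 7.3.3.4 does not use it. It treats a row whose end date was left blank in the middle of the sequence exactly like a dose still being taken at the last visit.

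Applied literally, this puts two doses on the same day, while the AUC formula has room for one. The plan does not say whether the later row, the higher row or the sum is used. The daily doses feed the first two OCS secondary endpoints, in active arms of 8 and a pooled placebo group of 12, where one patient's error is visible in the mean and in the responder counts.

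**Working it through.** The plan gives no OCS figure to reproduce, so the check applies its own formula to assumed dose histories. These are illustrations only.

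**Inputs.** Last visit Day 169 (Protocol Table 1). With the last infusion on Day 141 the dosing period ends on Day 171, so the last known OCS dose, Day 169, closes the window. Active arm n = 8 (Protocol 7.1.3). Assumed: 20 mg/day on Days 1–14, 15 on Days 15–28, 10 on Days 29–42, 5 from Day 43.

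**Formula (SAP 10.1.3).** With daily doses the trapezoid sum equals the total dose from Day M to Day N, minus half the first and last day's dose, divided by N − M. N − M is 168 from Day 1 and 118 from Day 51.

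**(a) First row (20 mg) has no end date.**
- Later row supersedes, which is the true history: total 14×20 + 14×15 + 14×10 + 127×5 = 1265 mg; (1265 − 12.5)/168 = 7.46 mg/day.
- Higher row kept: 20 mg on every day, so 20.00 mg/day.
- Rows summed: 20 mg extra on Days 15–169, 155×20 = 3100; (4365 − 22.5)/168 = 25.85 mg/day.

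The longest run at 5 mg or less is 127 days in truth and 0 under either overlap reading.

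**(b) A 14-day 20 mg course on Days 71–84, then 5 mg, with the course row left open.** The open row covers 85 extra days (Days 85–169).
- True: total 1265 + 14×15 = 1475. Day 1-on (1475 − 12.5)/168 = 8.71. Day 51-on total 119×5 + 210 = 805; (805 − 5)/118 = 6.78.
- Higher row kept: add 15×85 = 1275. Day 1-on (2750 − 20)/168 = 16.25. Day 51-on (2080 − 12.5)/118 = 17.52.
- Rows summed: add 20×85 = 1700. Day 1-on (3175 − 22.5)/168 = 18.76. Day 51-on (2505 − 15)/118 = 21.10.

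| Case (b), error in mg/day | Day 1-on, patient | Day 1-on, ÷8 | Day 51-on, patient | Day 51-on, ÷8 |
|---|---|---|---|---|
| Later row supersedes | 0 | 0 | 0 | 0 |
| Higher row kept | +7.54 | +0.94 | +10.74 | +1.34 |
| Rows summed | +10.06 | +1.26 | +14.32 | +1.79 |

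True runs at 5 mg or less are 28 days (Days 43–70) and 85 days (Days 85–169). Under either overlap reading only the 28-day run remains, so the 30- and 60-day criteria are lost. The 90- and 115-day criteria are not met even with the correct date.

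**Time to first relapse (SAP 10.1.5, item e).** In (b), if the increase was for sarcoidosis, the relapse is real and falls on Day 71 whether or not the end date is present. In (a), an overlap reading means the patient never reaches 5 mg, and the SAP then assigns 1 day and censors. Neither case creates or moves a relapse event.

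**Sensitivity of the Day 51-on error in one patient** (higher row kept / summed), 14-day course:
- 20 mg from Day 60: +12.1 / +16.2.
- 20 mg from Day 100: +7.1 / +9.4.
- 20 mg from Day 140: +2.0 / +2.6; the row then covers only 30 days in all.
- From Day 60, with start and course dose both 10 mg: +4.1 / +8.1; both 25 mg (weekly taper steps): +16.2 / +20.2.

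**The case against.** The best defence is that 7.3.3.4 was meant for a patient's current row. It pairs the missing end date with the word 'ongoing', it never says a later recorded dose is overridden, and 10.1.3 works with one dose per day and moves on to the next known one. A programmer who lets the later row supersede makes no error at all. An open middle row is also a correctable data error: diaries are reviewed at contacts and visits (Protocol 7.1.6.2 and 7.1.6.3), eCRFs are verified against source (Protocol 12.3), and the individual dose–time plots in SAP 10.1.6 could show it.

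Much of this stands as a limit on likelihood. It does not settle the text. The rule is unconditional, and the phrase about the next known dose defines the width of a trapezoid, not which of two overlapping rows is valid. The allowance in SAP 7.3.3.1 for substituting a more conservative date covers adverse events and concomitant medications, not this rule. SAP 7.3.3.3 promises queries for adverse event relationship and severity; 7.3.3.4 promises none.

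A reader might infer more than the documents support:
- That the plan instructs double-counting. It does not; summing is one of three possible readings, and the 26 mg/day figure belongs to that reading alone.
- That all patients are exposed. From Day 1 the log is the source only for patients without an eDiary, and daily entry largely protects the others.
- That false relapses follow. Neither worked case produces one.

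**Conclusion.** The concern holds in a limited form: SAP 7.3.3.4, followed literally, gives wrong daily doses for an open non-final row in the OCS log, and no other section corrects it. For one affected patient the Day 1-on time-adjusted AUC could be about 7.5, 20 or 26 mg/day in case (a), depending on an unstated programming choice. In case (b) the higher-row reading raises that patient's value by about 7.5 mg/day Day 1-on and 10.7 Day 51-on, moves an 8-patient mean by about 0.9 to 1.3 mg/day, and loses the 30- and 60-day criteria. A change in time to first relapse is not shown.

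These sizes rest on assumed dose histories, a window ending on Day 169 and exactly one affected patient in the arm. The number of log patients and the frequency of blank end dates are not in the documents, so the expected effect on the trial cannot be given. This is a minor point, worth correcting because the correction is nearly free.

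**What to change.** Replace the carry-forward rule in SAP 7.3.3.4 with this: any OCS record with no end date, including one marked 'ongoing', ends on the day before the start of the patient's next OCS record, unless concurrent use of both is documented; only the patient's final record is carried to the date of last visit.

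Including records marked as ongoing matters, because a stale row that a later row has replaced causes the same overlap. The exception keeps genuine concurrent use of two steroids from being erased.

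In case (a) the rule returns 7.46 mg/day; in case (b) it returns 8.71 (Day 1-on) and 6.78 mg/day (Day 51-on), with the 85-day run restored. The cost is one SAP sentence and one derivation line, with no effect on patients or trial conduct.

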7.3.3.5. Multiple Imputation for PFT Parameters

For PFT, sensitivity analyses will be performed to evaluate the impact of missing data. Where an analysis is specified as “Including Imputation”, it will be performed using the Multiple Imputation (MI) Fully Conditional Specification (FCS), using the proc mi procedure from SAS. The endpoints listed as “Key PFT endpoints” in Table 2 will be imputed by regressing on non-missing values of these variables at other timepoints. The number of imputations will be the percentage number of missingness. The following pseudo code will be used.

```
proc mi data=&pftparm._wide (where=( _NAME_ eq "FEV1PP")) seed=1234
  out=imputed_&pftparm._wide nimpute=pctmissing;
  fcs reg;
  var BASELINE WEEK_4 WEEK_8 WEEK_12 WEEK_16 WEEK_20 WEEK_24;
run;
```

Imputed values for Percent Predicted endpoints are restricted to 0 to 150 to ensure imputed values are consistent with values for patients with sarcoidosis and ensuring that impossible values are not produced (e.g. imputation of negative values).

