11.1.1.1. Mixed Model Repeated Measures Analysis (MMRM)

The absolute values specific parameters specified in Table 2 will be analyzed using a mixed linear model. Treatment and baseline are included as fixed effects. Repeated effect is included for visit. Restricted maximum likelihood method and Kenward and Roger (1997) method for degrees-of-freedom will be used. If a subject's baseline value is missing for a given parameter, then the subject is removed from that parameter's analysis.

This same analysis will be performed with and without multiple imputation as described in Section 7.3.3.5 Each individual/combined active arm will be compared with combined placebo arm.

Unstructured covariance structure will be used, but if convergence is not achieved, then compound symmetry (type=cs) covariance structure will be used.

The following pseudo code will be used.

```
proc mixed data = imputed method=reml;
  by _imputation_;
  class trt01p(ref='Placebo') avisit usubjid;
  model FEV1PP = trt01p avisit trt01p*avisit base / ddfm=kr;
  repeated / subject=usubjid type=un;
  lsmeans trt01p*avisit /pdiff=all cl;
  ods output diffs=lsmdiffl;
run;

proc mianalyze parms(classvar=full)=lsmdiffl;
  class trt01p _trt01p avisit _avisit;
  modeleffects trt01p*avisit;
  ods output ParameterEstimates=lsmdiffEstimate;
run;
```

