11.1.1.2. Random Coefficient Regression Model (RCRM)

Table 2 lists key variables that will also be analyzed in RCRM. This model will include treatment, baseline value and treatment-by-time interaction as fixed effects. Both intercept and continuous time in days are included as random effects. Unstructured covariance structures will be used for slope and intercept. If convergence is not achieved, then compound symmetry covariance structure (type=cs) is used and/or the random intercept may be removed. Restricted maximum likelihood and Kenward Rogers (1997) method for degrees-of-freedom will be used.

This same analysis will be performed with and without multiple imputation as described in Section 7.3.3.5. Each individual/combined active arm will be compared with combined placebo arm.

aTyr Pharma, Inc.
 Study ATYR1923-C-002 Statistical Analysis Plan
 IND#: 133692

FINAL Version 1.0
 2021-08-02

Pseudo code below will be used.

For comparing individual arms with placebo:

```
proc mixed data=imputed method=reml;
  class TRT01P(ref='Placebo') usubjid;
  by _imputation_;
  model &pftparm.=TRT01P BASE TRT01P*ady/noint solution ddfm=kr;
  random intercept ady/subject=usubjid type=un; *unstructured covariance
  structure had half of the trials not converge;
  estimate 'A_V_P' TRT01P*ady 1 0 0 -1/ CL;
  estimate 'B_V_P' TRT01P*ady 0 1 0 -1/ CL;
  estimate 'C_V_P' TRT01P*ady 0 0 1 -1/ CL;
  estimate 'T_V_P' TRT01P*ady 1 1 1 -3/ CL divisor=3;
  ods output Estimates=ran_coef_est(rename=(label=effect));
run;

proc mianalyze parms(classvar=full)=ran_coef_est;
  *class A_V_P B_V_P C_V_P A_V_B B_V_C A_V_C;
  modeleffects A_V_P B_V_P C_V_P A_V_B B_V_C A_V_C;
  ods output ParameterEstimates=rcrm_est;
run;
```

For combined active vs. placebo:

```
proc mixed data=imputed method=reml;
  class TRT01P(ref='Placebo') usubjid;
  by _imputation_;
  model &pftparm.=TRT01P BASE TRT01P*ady/noint solution ddfm=kr;
  random intercept ady/subject=usubjid type=un; *unstructured covariance
  structure had half of the trials not converge;
  estimate 'A_V_P' TRT01P*ady 1 0 0 -1/ CL;
  ods output Estimates=ran_coef_est(rename=(label=effect));
run;

proc mianalyze parms(classvar=full)=ran_coef_est;
  class A_V_P;
  modeleffects A_V_P;
  ods output ParameterEstimates=rcrm_est;
run;
```

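### The lung-function imputation stays within missing-at-random and leaves treatment out, so it cannot show the impact of missing data

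*SAP*

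**What the plan says.** SAP 7.3.3.5 gives the imputation a purpose, "For PFT, sensitivity analyses will be performed to evaluate the impact of missing data", and a method: fully conditional regression in which the key PFT endpoints "will be imputed by regressing on non-missing values of these variables at other timepoints". The pseudo-code names the variables: "var BASELINE WEEK_4 WEEK_8 WEEK_12 WEEK_16 WEEK_20 WEEK_24". There is no treatment variable, no BY statement and no shift for withdrawn patients. One further rule is that "Imputed values for Percent Predicted endpoints are restricted to 0 to 150".

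SAP 11.1.1.1 states the comparison: "This same analysis will be performed with and without multiple imputation as described in Section 7.3.3.5". SAP 11.1.1.2 says the same for the random coefficient model. The two analysis models are "model FEV1PP = trt01p avisit trt01p*avisit base / ddfm=kr" and "model &pftparm.=TRT01P BASE TRT01P*ady/noint solution ddfm=kr".

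No delta-adjusted, tipping-point, reference-based or other not-at-random (MNAR) analysis of PFT is specified in the SAP. The worsening rule under Table 2 deals only with missed visits between two low values, so it does not cover dropout.

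**The concern.** A sensitivity analysis for missing data should change the assumption about the values that were not seen. Here both runs keep it: the REML models and the imputation are each valid only if missingness depends on observed data. What does change between the runs is the treatment term, which has nothing to do with why data are missing.

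Both possible outcomes are therefore open to misreading. If the runs differ, the gap may be taken as the effect of missing data when it comes from filling gaps with a regression pooled over arms. If they agree, that may be taken as robustness when informative dropout has not been examined. Week 24 is one of the main PFT timepoints in SAP 11.1.1 and is where dropout accumulates. SAP 3.2 allows results to be used in regulatory submissions and manuscripts.

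**Working it through.** The plan gives no bias, power or dropout figure for this point, so there is none to reproduce. The check has five steps.

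**1. Variables side by side**

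| Model | Treatment | Treatment by time | PFT values used | Assumption |
|---|---|---|---|---|
| Imputation (7.3.3.5) | no | no | baseline, Weeks 4 to 24 | MAR |
| MMRM (11.1.1.1) | yes | yes | baseline as covariate, all visits | MAR |
| RCRM (11.1.1.2) | yes | yes (slope in days) | baseline as covariate, all visits | MAR |

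**2. Direction of the distortion.** Let p be the fraction missing at Week 24, Δ the true difference, and λ the share of Δ that a pooled regression recovers through earlier observed values. Approximately:

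estimate = (1 − p)Δ + pλΔ = Δ[1 − p(1 − λ)]

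Without arm, λ < 1 and the estimate shrinks. With arm, λ is about 1 and it does not.

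**3. Size.** Simulated Week 24 difference, 2:1 allocation, six post-baseline visits. Assumptions: SD 15 points, true effect 5 points growing linearly to Week 24, correlation parameter 0.7 or 0.9, monotone dropout at random. The first two blocks used 2,400 active and 1,200 placebo patients to expose the systematic part. The third is a separate run under its own assumed variances and a true effect of 5.

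| Run | Dropout | Reference | Imputation as written | Shrinkage |
|---|---|---|---|---|
| 0.7, reference MMRM | 10% | 5.27 | 4.91 | 0.36/5.27 = 7% |
| | 20% | 4.98 | 4.20 | 0.78/4.98 = 16% |
| | 30% | 4.93 | 3.84 | 1.09/4.93 = 22% |
| 0.9, reference MMRM | 10% | 5.17 | 4.83 | 0.34/5.17 = 7% |
| | 20% | 5.30 | 4.61 | 0.69/5.30 = 13% |
| | 30% | 4.81 | 3.86 | 0.95/4.81 = 20% |
| Separate run, reference imputation with arm | 10% | 5.00 | 4.69 | 0.31/5.00 = 6% |
| | 20% | 4.95 | 4.33 | 0.62/4.95 = 13% |
| | 30% | 4.91 | 3.98 | 0.93/4.91 = 19% |

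With arm added (0.9), imputation gave 5.17, 5.30 and 4.80 against MMRM 5.17, 5.30 and 4.81. The 0 to 150 limit was applied in both versions, so it does not explain the shrinkage.

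At the trial's size (24 v 12, parameter 0.9, 60 replicates, 10 imputations), the mean absolute gap from MMRM was 0.52, 1.13 and 1.60 points as written, and 0.37, 0.58 and 0.77 with arm. In a single trial the gap thus mixes the omitted arm with imputation noise.

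**4. Response to informative dropout.** If unseen values are lower by δ, the true difference changes by about −(δ_active × p_active − δ_placebo × p_placebo). With 20% dropout and a shift in active patients only, that is 0.20 × 5 = 1.0 or 0.20 × 10 = 2.0 points.

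| Shift in active dropouts | Truth | MMRM | Imputation with arm | Imputation as written |
|---|---|---|---|---|
| −5 | 3.86 | 4.91 | 4.87 | 4.26 |
| −10 | 2.82 | 4.85 | 4.89 | 4.32 |

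The truth moves by 1.04 points and none of the three estimates follows it. This is by construction: the observed data do not depend on the shift, so only a changed assumption can reveal it. With equal shifts and equal dropout in both arms the effect cancels: 0.20 × 5 − 0.20 × 5 = 0.

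**5. A one-sided scenario.** Assumptions: patient SD 14, SD of individual Week 24 change 5, error SD 3, no true effect, and 30% dropout per visit when the unobserved value is more than 5 points below baseline, in active patients only. About 24% of them are then missing at Week 24. The MAR likelihood estimate was 0.73 against 0.07 with complete data, too favourable by 0.66; imputation with arm gave 0.72. A 4,000-trial rebuild gave 0.84. With the same rule in both arms the bias was 0.03 to 0.04. With the triggering value observed it was 0.02.

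Limits: the simulations used maximum likelihood rather than REML with Kenward-Roger, and sequential regression in place of fully conditional specification. The RCRM was not simulated.

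**The case against.** The strongest reply is that little hangs on this. PFT endpoints are exploratory (SAP 4.2.3), and SAP 7.4.1 and 7.5 plan no formal tests and no multiplicity control, so no decision can tip. Informative dropout is also not established. Protocol 7.1.6.3 permits rescue steroids and keeps rescued patients on study drug and in follow-up. Protocol 6.4.1 and 6.4.2 bring those who stop back for the end-of-study visit, where PFT is measured. No stopping rule refers to lung function. Some missing visits will be due to COVID-19 (Protocol 6.3.1) and need not be informative.

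Most of that stands, and it limits the severity. It does not rescue the stated purpose of 7.3.3.5. Protocol 2.1 says relapse is common once steroids are tapered, intermediate visits can still be lost after stopping, and informative dropout is the case a sensitivity analysis exists to examine.

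A reader might also infer that the imputation merely repeats the mixed model from the same variables, so that agreement is guaranteed. The documents do not support this. Treatment is in both analysis models and absent from the imputation. Smaller differences are the 0 to 150 limit, the compound-symmetry fallback, the linear time trend in the RCRM, and nominal days for imputed records (SAP 7.3.4). Repetition would hold, on average, only for an MMRM imputation with arm included.

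**Conclusion.** The concern holds on two counts. First, the imputation omits treatment and is not compatible with the models it feeds. The direction, toward no difference, follows from the omitted term. The size, about 6 to 22% at 10 to 30% dropout, depends on the assumed variances, correlations, effect of 5 points and dropout rates, none of which the documents supply. Second, repairing that would still leave the plan with MAR analyses only, so the promised evaluation would remain undelivered.

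A reader might go further and conclude that the trial's PFT estimates will be too favourable by some 0.7 to 0.8 points. The documents do not support that. The figure needs dropout in active patients alone, triggered by a value never seen, while the steroid taper applies to both arms. Even then, 0.66 is about 0.3 of the simulated SD of the estimate (0.66/2.3). It is a one-sided scenario, not a forecast.

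The change should be made, but nothing primary or secondary depends on it.

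**What to change.** 1. Add treatment arm to the PROC MI model as a class covariate. Do not impute separately by arm. With 8 patients per active arm, an intercept and six other timepoints use 7 parameters and leave at most 8 − 7 = 1 residual degree of freedom. As a covariate, four arms add three indicators: 10 parameters on up to 36 patients.
2. Add a delta-adjusted run (the MNAR ADJUST statement in PROC MI) that shifts imputed post-withdrawal values over a short pre-specified range, such as 0, 2.5, 5 and 10 percent-predicted points, once in active arms only and once in both arms. Report how the Week 24 estimate and its confidence interval change. With no decision rule there is no threshold to tip. Label the shifts as analyst assumptions, since the documents offer no source for them.
3. Keep the un-imputed MMRM and RCRM as the main PFT analysis.

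Steroid dose is not worth adding as an auxiliary predictor. SAP 7.3.3.4 does not impute it and carries ongoing doses only to the last visit, so it runs out where PFT values do.

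The cost is a few lines of code, a withdrawal flag by visit and one table, with several exploratory estimates to report instead of one. If the sponsor prefers not to add the run, the minimum is to add arm and remove the claim that the imputation evaluates the impact of missing data.

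### The multiple imputation for lung function omits treatment, so the imputed MMRM and RCRM contrasts are biased, in a direction that depends on how the effect develops over time

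*SAP*

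**What the plan says.** SAP 7.3.3.5 states the purpose: "For PFT, sensitivity analyses will be performed to evaluate the impact of missing data". The method is fully conditional specification in PROC MI. By the text, the key endpoints of SAP Table 2 "will be imputed by regressing on non-missing values of these variables at other timepoints". The code agrees with the text: "var BASELINE WEEK_4 WEEK_8 WEEK_12 WEEK_16 WEEK_20 WEEK_24". It has no treatment variable, no CLASS statement and no BY treatment statement, and no other section of the SAP adds treatment to this step. The BY lines in SAP 11.1.1.1 and 11.1.1.2 loop over completed data sets at the analysis step.

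The models run on those data sets do contain treatment. The MMRM code is "model FEV1PP = trt01p avisit trt01p*avisit base / ddfm=kr". For the RCRM, SAP 11.1.1.2 says: "This model will include treatment, baseline value and treatment-by-time interaction as fixed effects". For both, each dose arm and the combined active arm are compared with combined placebo, and results are shown both ways. In the words of SAP 11.1.1.1: "This same analysis will be performed with and without multiple imputation as described in Section 7.3.3.5".

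**The concern.** An imputation model should contain at least the terms that the analysis model estimates. Here it is narrower. A placebo patient and an active patient with the same observed values have the same distribution of imputed values, so treatment can enter an imputed value only through what the patient's other visits already carry. A patient with nothing after baseline contributes an expected arm difference of zero.

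At stake is the reading of the sensitivity analysis. If the imputed contrast is smaller than the non-imputed one, a reader would suppose that missing data weaken the lung-function signal, when the gap may come from the imputation model alone. Week 24 is among the main timepoints in SAP 11.1.1. Protocol 6.3.1 anticipates delayed or missed visits and withdraws patients who miss two consecutive doses, so late missing values are plausible.

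**Working it through.** The plan states no figure for this point, so there is none to reproduce.

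**From the documents:** 2:1 allocation, 24 active and 12 placebo; baseline plus six visits; treatment absent from the imputation and present in both analysis models.

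**Assumed:** 10, 20 or 30% missing at Week 24, completely at random, with monotone dropout spread evenly over the last observed visit (baseline to Week 20); Week 24 effect of 0.5 SD; compound-symmetry correlation of 0.8 to 0.95, or AR(1) at 0.95.

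**Large-sample formula.** Let δ be the vector of true arm differences by visit, Σ the within-arm covariance and p = 2/3. Pooling the arms gives covariance Σ + p(1−p)δδ′ with p(1−p) = 2/9. For a patient last seen at visit k, the imputed Week 24 difference is B·δ(observed), where B comes from that pooled covariance. Call its ratio to the true difference r(k). With fraction f missing, estimated/true = 1 − f(1 − r̄), where r̄ is the mean of the six r(k).

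**Example: constant effect, correlation 0.8, last seen at Week 4.**
- Pooled variance at Week 4: 1 + (2/9)(0.25) = 1.0556.
- Pooled covariance of Weeks 4 and 24: 0.8 + 0.0556 = 0.8556.
- Coefficient on Week 4, adjusting for baseline: (0.8556 − 0.64)/(1.0556 − 0.64) = 0.519, so r = 0.519.
- The six values, last seen at baseline through Week 20, are 0, 0.519, 0.683, 0.764, 0.812 and 0.843, with mean 0.603.
- At 10/20/30% missing: 1 − 0.1(0.397) = 0.960, then 0.921 and 0.881.

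**Estimated/true over all the assumed correlations:**

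| Effect shape | 10% missing | 20% | 30% |
|---|---|---|---|
| Constant | 0.96–0.98 | 0.92–0.95 | 0.88–0.93 |
| Growing linearly | 0.92–0.94 | 0.84–0.88 | 0.77–0.82 |
| Late (half at Week 20, full at Week 24) | 0.90–0.91 | 0.80–0.82 | 0.71–0.73 |
| Waning (twice as large early) | 0.99–1.00 | 0.98–0.99 | 0.97–0.99 |

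With treatment in each visit's regression the ratio is 1.00. If only Week 24 is missing, r is 0.84 to 0.97 for a constant effect but 1.04 to 1.20 for a waning one, so the bias can run away from zero.

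**Other variance assumptions** (between-patient SD 14, visit SD 4, random-slope SD 3, true effect 5, 400,000 patients, dropout from Week 8), at 10/20/30% missing:
- Immediate effect: 4.92/4.84/4.75, an attenuation of 1.6 to 5%.
- Linear effect: 4.67/4.35/4.02, or 7 to 20%.
- Late effect: 4.55/4.10/3.65, or 9 to 27%.

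A separate run under these variances gave 3.95 (linear) and 3.55 (late) at 30% missing, about 5.0 with treatment added, and 5.32 for a waning effect.

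**At N = 36** (SD 15, correlation 0.9, true effect 5, 1,000 replicates, Week 24 ANCOVA standing in for the MMRM contrast; Monte Carlo SE 0.07–0.09), at 10/20/30% missing:
- Constant effect: 4.77/4.63/4.53 without treatment, 4.96/5.04/5.23 with it.
- Growing effect: 4.72/4.11/3.79 without, 5.15/4.94/4.99 with.
- Waning effect: 4.85/5.04/5.06 without, 4.86/5.08/5.12 with.

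**The case against.** The strongest reply is that little depends on this. The imputed runs are sensitivity analyses of exploratory endpoints, SAP 7.4.1 excludes formal hypothesis testing, and the same models appear without imputation and with treatment in them. That stands, and it limits the point to the imputed runs.

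The reply also has force on precision. A second simulation at 36 patients used the SD 14/4/3 variances, the four-level arm variable, five imputations and 1,500 replicates. At 10 to 20% missing the attenuation was 0.1 to 0.6 points against a sampling SD of about 2.2. At 30% missing with a linear effect, mean and root mean squared error were 3.86 and 2.50 without treatment, against 4.93 and 2.74 with it. So the fix does not lower total error there. It removes a systematic difference between two analyses that are meant to be compared.

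If active dropouts lose the drug effect, the true value is 3.97 at 20% dropout under the linear assumptions. Imputation with treatment gives 4.98, while the SAP's version should give about 4.35 and so lies closer. That closeness is incidental: the SAP does not say that its imputation targets loss of effect.

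A reader might infer that the contrast is always pulled toward zero, or that the bias peaks at Week 24 because most data are missing there. The documents support neither. Direction depends on the effect's shape and the missingness pattern, and no missingness rate is given. Imputation also uses later visits where they exist, so isolated missed visits differ from the monotone dropout modelled here.

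**Conclusion.** The omission is certain, because text and code agree. The imputed MMRM and RCRM contrasts are biased: toward zero for a constant, growing or late effect, and near nil or away from zero for a waning one. The attenuation is roughly 1 to 12%, 6 to 23% and 9 to 29% respectively for the first three shapes. These sizes rest wholly on the assumed variances, effect shapes and 10 to 30% missing at Week 24. The upper end needs both 30% missing and a late effect.

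The consequence is that the comparison with and without imputation cannot isolate the impact of missing data. It would be wrong to conclude that the trial's lung-function results as a whole are biased: the non-imputed models do not share the fault, and neither do the primary safety endpoint or the OCS endpoints. The change is worth making but is not critical.

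**What to change.** Carry treatment into the wide data set and add it to the imputation model, with placebo combined: `class trt01p; fcs reg; var trt01p BASELINE WEEK_4 ... WEEK_24;`. Use the four-level arm variable for the individual-dose contrasts and a two-level variable for combined active versus placebo. Amend the sentence in SAP 7.3.3.5 to match. Do not impute separately by arm: 8 patients per dose arm cannot support regressions with up to seven parameters.

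The cost is SAP wording, a few lines of SAS and up to three extra parameters per regression. The precision loss is not trivial. In the second N = 36 simulation, at 30% missing with the four-level variable, the SD of the estimate rose from 2.23 to 2.74 (linear effect) and from 2.32 to 2.76 (immediate effect), about 20%.

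Optional and separate: the corrected imputation still assumes missing at random, as the MMRM does. It may differ from the MMRM in detail, for example because it can fill a missing baseline that the MMRM would drop, but it does not test that assumption. A delta-adjusted run with prespecified shifts would be needed to probe departures from it.
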